**Statistical Analysis Plan**

---

a3: number of times agreement on event but INV declares event earlier than IRC Review;  
 $N = a+b+c+d$ .

The following measure of discordance will be calculated per arm:

- Total Event Discrepancy Rate:  $(b+c) / N$
- Early Discrepancy Rate (EDR):  $(a3+b) / (a+b)$
- Late Discrepancy Rate (LDR):  $(a2+c) / (a2+a3+b+c)$
- Overall Discrepancy Rate:  $(a2+a3+b+c) / N$

A window of 28 days will be used in determining agreement on timing of an event. Specifically, if the data or recurrence by the IRC is within +/- 28 days of the data of recurrence by the investigator these cases will be considered as ‘agreement on the timing and occurrence or an event’.

- DFS based on IRC Without Censoring for New Cancer Therapy or Missed Assessments: DFS based on IRC review, as defined for the primary analysis, but without censoring subjects who:
  - receive further anti-tumor therapy, or
  - have two or more consecutively missed or not readable scans immediately prior to recurrence, or occurrence of a secondary malignancy, or death.

In other words, a subject who meets the above criteria will be assigned a DFS event at the first date of recurrence or occurrence of a second primary cancer or death. In the absence of a DFS event, DFS time will be censored at the date of last scan prior to the time of analysis. Subjects alive who do not have post-baseline disease assessment will have their DFS times censored at randomization. (Refer to Table 4 of Appendix A for censoring rules.)

- Start of New Anti-tumor Therapy as DFS Event: DFS based on IRC review, as defined for the primary analysis, but utilizing the start date of new anti-tumor therapy as a DFS event. (Refer to Table 5 of Appendix A for censoring rules.)
- DFS at Scheduled Assessments: DFS based on IRC review, as defined for the primary analysis, but instead assigning the dates for events and censoring at the scheduled scan dates instead of the actual scan dates. Specifically, events that occur within +/- 4 weeks of a scheduled scan will be considered an event at the scheduled scan. Events outside the 4-week window will be counted as events at the next scheduled scan time and censoring outside the 4-week window would be censored at the previous scheduled scan. If, however, the event is death or disease at baseline, the date of death or date of randomization respectively will be used as the event date unless anti-tumor therapy was

---

|           |   |                 |           |
|-----------|---|-----------------|-----------|
| Document: | C:\Users\q764206\AppData\Local\Microsoft\Windows\Temporary Internet Files\Content.Outlook\GWW33WM3\ATLAS_SAPFinal v8.0_06MAR2018.docx |                 |           |
| Author:   | [name] (Updated [name]; [name]; [name], [name])  | Version Number: | Final 8.0 |
|           |   | Version Date:   | 06MAR2018 |

Template No: CS\_TP\_BS016 – Revision 2  
 Effective Date: 01Feb2010

Reference: CS\_WI\_BS005

**Statistical Analysis Plan**

---

received prior to the date of death in which case the subject will be censored at the scheduled scan prior to the date of anti-cancer therapy or for subjects who have two or more missed or not readable consecutive tumor scans immediately followed by an event will be censored on the date of their most recent scheduled scan prior to the missing/not readable scans. (Refer to Table 6 of Appendix A for censoring rules.)

- DFS with Interval-censoring: DFS based on IRC review as defined for the primary analysis will be performed with a parametric model utilizing techniques for interval-censored data. Graphical diagnostics will be used to select the distribution of the parametric model that best fits the data. Intervals of 16 weeks will be implemented for censoring purposes (Refer to Table 7 of Appendix A for censoring rules.)

**7.3.2. Subgroup Analyses**

In addition, DFS by IRC will be analyzed in the same way as the primary analysis for the following subgroups with the exception that there will be no stratification variable in the model due to small numbers of subjects:

- Risk group
  - i. a (pT2/pN0 or pNX/M0)
  - ii. b (pT3/pN0 or pNX/M0)
  - iii. c (pT4/pN0 or pNX/M0)
  - iv. d (Any pT/pN1/M0)
  - v. c+d combined
  - vi. High Risk ([b with Fuhrman grade 3 or 4]+c+d)
  - vii. Low Risk (a+[b with Fuhrman grade 1 or 2])
- Age (<65, >=65 years)
- Race
- Gender
- Baseline ECOG PS (0 vs >=1)
- Baseline Weight
  - viii. Normal (18.5<=body mass index (BMI)<25)
  - ix. Overweight + Obese (BMI>=25)
  - x. Overweight (25<=BMI<30)
  - xi. Obese (BMI>=30)
- Baseline neutrophil to lymphocyte ratio (NLR) (NLR>3 vs. NLR<=3)
- Fuhrman Grade (1&2 vs. 3 &4)

---

Document: C:\Users\q764206\AppData\Local\Microsoft\Windows\Temporary Internet Files\Content.Outlook\GWW33WM3\ATLAS\_SAPFinal v8.0\_06MAR2018.docx  
 Author: [name] (Updated [name]; [name]; [name], [name])      Version Number: Final 8.0

Version Date: 06MAR2018

Template No: CS\_TP\_BS016 – Revision 2  
 Effective Date: 01Feb2010

Reference: CS\_WI\_BS005

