**6.5. Multiple Comparisons/Multiplicity**

For the interim analysis performed and the final analysis for the primary endpoint of DFS, the significance level has been set using the O’Brien-Fleming method. Although there is no intention to perform any hypothesis test for OS at the interim analysis, a nominal  $\alpha$  of 0.0001 will be allocated to the analysis of OS at the interim. There will be no other adjustments for multiple testing.

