**7. Statistical Analysis**

**7.1. Analysis of Primary Efficacy Endpoint**

**7.1.1. Disease-Free Survival Based on IRC Review**

Disease-Free Survival of the ITT Population based on the IRC review of tumor assessments will be summarized using the Kaplan-Meier method. Kaplan-Meier curves for each arm will be generated, and median DFS time will also be presented with corresponding 95% CI. The CI for the median will be calculated according to Brookmeyer and Crowley. To test the equality of DFS time in each arm a stratified log-rank test (using a stratification factor as defined in Section 5.4) will be used. Censoring rules as described in Table 1 of Appendix A will be implemented. The statistic of the test will be presented along with the associated two-sided p-value.

The estimated HR (Axitinib/Placebo) will be obtained using a Cox’s Proportional Hazards model with treatment group as well as a randomization stratification factor as a covariate. The stratification factor used in the analyses will be risk group as described in Section 5.4.1.

The significance level for the final DFS analysis will be 0.0442 as calculated using the O’Brien-Fleming method. (Assumes interim analysis at 184 events with a significance level of 0.0194).

Annual DFS rates up to 5 years for each treatment group will be estimated and presented with corresponding 95% CI. The CI for the survival function will be calculated using the complementary log-log transformation method.

The final analysis of the primary endpoint of DFS will be performed when approximately 245 DFS events based on IRC review are observed.

A subject listing for DFS will include, DFS time, censoring status, censoring reason, date of randomization and date of last tumor assessment. In addition, a listing of subjects with baseline disease as determined by the IRC, will be produced.

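### SAP 7.3.2 tests DFS separately in each subgroup with no treatment-by-subgroup interaction and no event minimum, so subgroup p-values can suggest differences that are not there

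*SAP*

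**What the plan says.** SAP 7.3.2 states that DFS by the Independent Review Committee (IRC) "will be analyzed in the same way as the primary analysis for the following subgroups". The only exception is that "there will be no stratification variable in the model due to small numbers of subjects". The method carried over is that of SAP 7.1.1: Kaplan-Meier curves and medians, a Cox hazard ratio, and a log-rank test, of which it says "The statistic of the test will be presented along with the associated two-sided p-value".

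The list in 7.3.2 contains:

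- seven risk-group cuts (a, b, c, d, c+d, High Risk, Low Risk), which overlap;
- four weight levels, of which overweight-plus-obese overlaps with overweight and with obese;
- two levels each of age, gender, ECOG performance status, neutrophil-to-lymphocyte ratio and Fuhrman grade;
- race, with no levels given.

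That is 7 + 4 + 10 = 21 named levels plus race, or 23 if race has two levels.

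SAP 6.5 sets the interim and final levels for DFS and an interim allocation for OS, then says "There will be no other adjustments for multiple testing". Neither document contains a treatment-by-subgroup interaction test, a minimum subgroup size, or a rule for reading the subgroup results. By contrast, SAP 7.3.4 withholds the p-value from the one-year landmark analysis because that analysis is exploratory.

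**The concern.** A p-value inside one subgroup asks whether axitinib works in those patients. It does not ask whether the effect differs from that in other patients. Given only separate p-values, a reader will tend to set a significant level against a non-significant one, for example High Risk against Low Risk, and take the contrast as evidence of a difference. With 245 events divided among subgroups, that contrast arises often by chance when the effect is the same in everyone. At stake is a false statement about who benefits, in either direction: a responsive group that is not special, or a group written off because it had few events. The smallest cell, group c, would receive a p-value and a median based on a handful of events.

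**Working it through.** **The plan's own figures.** SAP 3.3 gives 245 events for 90% power at HR 0.654, two-sided 0.05.

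- Freedman: ((1 + 0.654)/(1 − 0.654))² × (1.960 + 1.282)² = 241 events.
- Schoenfeld: 4 × (1.960 + 1.282)² / (ln 0.654)² = 234 events.
- Freedman is within 3% of 245. The critical HR at the final level of 0.0442 is exp(−2 × 2.012/√245) = 0.773, as the SAP states.

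**One two-level factor, HR 0.654 in both levels.** Power with d events is Φ(√d/2 × |ln 0.654| − 1.96), with |ln 0.654| = 0.425. The chance of a split verdict is p1(1 − p2) + p2(1 − p1).

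| Split of 245 events | Power, larger level | Power, smaller level | Split verdict |
|---|---|---|---|
| 50:50 | 0.652 | 0.652 | 45% |
| 70:30 | 0.794 | 0.444 | 53% |
| 80:20 | 0.844 | 0.318 | 62% |

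**Several factors together.** The factors share the same patients, so these chances cannot be multiplied, and simulation was used with 1,000 trials per setting. From the documents: 700 patients, 1:1 allocation, 24 months' accrual, 23% drop-out by 18 months, placebo hazards from the 2-year DFS rates, analysis at 245 events. Assumed: risk groups 10/80/1/9% (the plan gives 90% for a and b together and a cap of about 10% on a); two race levels; two-level factors split 50:50, 70:30 or 80:20; BMI mix 3/47/37/13%; factors not prognostic apart from risk group, and independent except that High/Low Risk is built from Fuhrman grade. Eight complementary pairs were compared: High/Low Risk, normal against overweight-plus-obese, age, race, gender, ECOG, neutrophil-to-lymphocyte ratio and Fuhrman grade. Significance means p<0.05 in favour of axitinib.

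| True HR, same in everyone | At least one of eight pairs split | Some of 23 subgroups significant, others not |
|---|---|---|
| 0.654 | 85–96% | 98% |
| 0.773 | 77–78% | 82–84% |
| 0.87 | 50–51% | 58% |
| 1.0 | 18–22% | 26–30% |

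With no effect at all, at least one of the 23 subgroups reaches p<0.05 in either direction in 49–52% of trials.

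**Smallest groups.** Group c is planned at 1%, so 0.01 × 700 = 7 patients and about 4 events. Its power at HR 0.654 is Φ(√4/2 × 0.425 − 1.96) = 6%. Group d has about 39 events and 26–27% power.

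**Interaction tests instead.** With 245 events split 50:50, the standard error of the log ratio of HRs is √(4/122.5 + 4/122.5) = 0.256. Power is Φ(|ln ratio|/0.256 − 1.96): 77%, 52% and 29% for ratios of 0.5, 0.6 and 0.7. Under a uniform effect each test flags about 5% of the time (simulated 4.3–5.5%). At least one of eight flags in about 30–36%; if independent, 1 − 0.95⁸ = 34%.

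**Stratification.** The assumed placebo hazard in group d is ln 0.33/ln 0.70 = 3.1 times that of a and b pooled. Even so, in 400 simulated trials under the plan's hazards the overall HR averaged 0.668 unstratified and 0.656 stratified.

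**The case against.** The strongest case on the other side has five parts.

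- *No decision rests on these analyses.* They fall under additional efficacy analyses (SAP 7.3). Alpha goes only to DFS by IRC and, if DFS is significant, to OS. This stands. A reader might infer from SAP 6.5 that the subgroups inflate the trial's error rate; they do not, and unadjusted supportive subgroups are common.
- *The harm depends on how results are read.* A reader might infer that a uniform effect will almost always look heterogeneous. That needs the full design effect, the assumed splits and a comparison of p-values. The documents do not say that subgroups will be read that way. By direction of effect, at HR 0.654 some subgroup with at least 20 events shows an HR above 1 in only 35–53% of trials. This limits the claim without removing it, since the plan supplies p-values and nothing better.
- *The display cannot be checked.* Table and figure shells are listed in the SAP contents but are not in the text available, so a forest plot may already be specified. That is possible. However, 7.3.2 exempts only stratification from the primary method, so the p-value follows from its wording.
- *Dropping stratification is stated and reasoned* (SAP 5.4.1 and 7.3.2), and stratifying by risk group within a, b, c or d means nothing. This largely stands. The reason of small numbers fits the age or gender subgroups poorly if, as is likely, these hold hundreds of patients, but the effect on the HR is small.
- *Interaction tests bring false flags and low power of their own.* True, and the proposed text must say so.

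**Conclusion.** The point holds as a weakness in how subgroup results will be interpreted, and SAP 7.3.2 should be changed. The primary DFS analysis and its type I error are untouched. At a uniform HR of 0.654, and reading by p-value, a single two-level factor gives a split verdict in about 45–62% of trials, and at least one of eight factors does so in about 85–96%. These ranges rest on assumed subgroup splits, two race levels and near-independent factors, and the frequency falls as the effect weakens. Uniformity is itself an approximation: the plan assumes HRs of 0.66, 0.47 and 0.61 by category, though 90% of patients share 0.66. The figures do not show that subgroups will mislead in nearly every trial whatever the true effect. Nor do they show that the missing stratification is the cause; small event counts and separate testing are. For group c, with about 4 events, the p-value and median carry essentially no information.

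**What to change.** Revise SAP 7.3.2 as follows.

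1. Present the HR, 95% CI and events/N for each subgroup, for example in one forest plot, without subgroup p-values. This matches how SAP 7.3.4 treats the landmark analysis.
2. For each factor, on non-overlapping levels, give one treatment-by-factor interaction from a Cox model on the ITT population, stratified by risk group (unstratified when the factor is risk group or High/Low Risk). Report it as a ratio of HRs with 95% CI and label it exploratory.
3. State the levels: for example a, b and c+d for risk group; normal against overweight-plus-obese for weight, saying what happens to patients with BMI below 18.5, who are in no listed level; and the levels of race.
4. Do not estimate an HR or median in a level below a pre-stated event minimum, for example 10. The exact number is a judgement.

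The cost is a few lines of text and eight or nine extra models, with no new data and no change to the primary analysis. The drawbacks belong in the SAP: power is about 52% for a ratio of HRs of 0.6 at a 50:50 split, so many results will be inconclusive, and eight unadjusted tests will flag at least one factor in about 30–36% of trials when the effect is uniform.

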**Statistical Analysis Plan**

---

**7.3.3. Post hoc Analyses**

In addition to the overall analysis, all efficacy and safety analyses may later be presented by country in order to produce results to be included in Japan, China, Korea and Taiwan sub-population reports. The decision to pursue these analyses will be determined by SFJ depending upon availability of subjects within country strata. There are no other planned subset analyses in this study.

**7.3.4. Exploratory Analyses**

Exploratory analyses may be performed as deemed appropriate.

RMST for DFS may be explored if non-proportional hazards are observed for the primary endpoint.

DFS and Treatment Duration: A one-year landmark analysis will be performed to explore the association between extended treatment with Axitinib and DFS. Patients randomized to Axitinib will be divided into 2 groups based on treatment status at 1 year. Namely patients whose duration of treatment in less than or equal to one year will be compared to those whose duration of treatment is greater than one year. Only patients randomized to treatment with Axitinib who are alive, disease-free, and still in disease-free survival follow-up at one year will be included in the analysis. Specifically, patients who had disease recurrence, secondary malignancies, died, or were otherwise censored for DFS due to start of new anticancer therapy, missed assessments, or lost to follow-up prior to one year will be excluded from the analysis. Median event times and 2-sided 95% CIs for each median will be provided based on the Brookmeyer-Crowley method. Cox proportional hazards model will be used to estimate the unstratified hazard ratio and its 95% CI. A p-value will not be reported as this analysis is considered exploratory.

Treatment Discontinuations due to AEs of Interest: an evaluation of cumulative incidence of treatment discontinuations for defined AEs of interest will be conducted. A summary table will be provided. A figure displaying the proportion of subjects off treatment over time will be provided for subjects randomized to axitinib or placebo who experienced various defined adverse events of interest.

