#### 6.5.1. Withdrawal from treatment

Patients will be withdrawn from treatment in the case of:

- Recurrence or occurrence of a secondary malignancy. Investigators are encouraged
  to await the result of the IRC assessment before making treatment decisions unless
  clinical considerations require immediate intervention eg, in the case of brain
  metastases;
- Unacceptable toxicity;
- Need for anticancer therapy not specified in the protocol;
- Congestive heart failure;
- Repeated noncompliance;
- Patient becomes pregnant;
- Patient lost to follow-up;
- Patient choice to withdraw from treatment (follow-up permitted by patient)

If patients require >2 consecutive weeks of dose interruption, a discussion should be made in consultation with the medical monitor.

Data to be collected for the end of study treatment/withdrawal from treatment are described in the End of Study Treatment/Withdrawal from treatment Procedures section (Section 6.2.3). Patients will be followed up for at least 28 days after the last dose of study drug for adverse events and concomitant medications and treatments

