#### 7. ASSESSMENTS

#### 7.1. Efficacy Assessments

Local and the IRC imaging tumor assessments are to be performed between week 3-8 post-nephrectomy. Brain CT or MRI within 12 weeks prior to randomization is acceptable regardless of whether it is before or after nephrectomy.

During the trial, local and the IRC imaging tumor assessments will be performed (regardless of the duration of treatment) every 16 weeks during the first 3 years of study (also, at the end of treatment) and every 6 months thereafter until the time for final analysis, or recurrence or occurrence of a secondary malignancy, whichever comes first.

Investigators are encouraged to await the result of the IRC assessment before making treatment decisions for patients who require palliative radiotherapy because of suspected recurrence or occurrence of a secondary malignancy unless clinical considerations require immediate intervention eg, in the case of brain metastases. In the event that an investigator determines recurrence or occurrence of a secondary malignancy based on local imaging reviews and/or local histo-/cytopathology reports, the patient must continue to receive tumor assessments until the IRC determines recurrence or occurrence of a secondary malignancy.

Local and IRC imaging assessments at screening and during the trial will include CT or MRI of the brain, chest, abdomen and pelvis, and other applicable sites. Further imaging techniques e.g., bone scan, are to be performed as clinically indicated if metastases are present or suspected.

For patients who present with findings suggestive of a tumor recurrence or secondary malignancy, histo-/cytopathological confirmation of the diagnosis should be obtained except in patients whose suspicious lesions are deemed by the investigator not to be amenable to biopsy. Such available local histo-/cytopathology reports should be submitted to the IRC for review in cases for which there is site confirmation of recurrence or occurrence of a secondary malignancy in the absence of IRC imaging confirmation. For patients with an isolated, suspected intracranial recurrence, histologic documentation of recurrence in surgically accessible lesions is highly recommended, but not required. For such patients, document the recurrent disease using MRI or CT if MRI is not generally available or is contraindicated.

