## 5. Efficacy Endpoints and Covariates

### 5.1. Primary Efficacy Endpoint

The primary endpoint is DFS, defined as the time interval (measured in years) from the date of randomization to the first date of recurrence (distant or local recurrence of RCC) or the occurrence of a secondary malignancy or death due to any cause. The primary DFS analysis will be based on assessment by the IRC. The IRC will review all available scans and in cases for which there is site confirmation of recurrence or occurrence of a secondary malignancy in the absence of IRC imaging confirmation, available local histo-/cytopathology reports will be reviewed by an independent IRC oncologist.

Recurrence refers to relapse of the primary tumor in situ or at metastatic sites. The date of recurrence or the occurrence of a secondary malignancy is defined as the earlier of:

- the date of the tumor scan or the date of collection of the histo-/cytopathological specimen (for subjects who have site confirmed recurrence or occurrence of a secondary malignancy in the absence of IRC imaging confirmation) that demonstrated unequivocal recurrence or a second malignancy according to protocol criteria

Per the IRC charter, radiological findings should be unequivocal. At the time of the final IRC review for a given data cut (interim or final), equivocal disease, identified by radiology requiring confirmation, is noted in the IRC data at the ‘Global Review’ with an indication of disease present and a date of recurrence/secondary malignancy recorded by the IRC as not applicable (N/A). As these findings require confirmation, they will not be counted as events in the DFS analysis unless, there is a subsequent pathology report which provides confirmation of the disease seen on the scan. In this case the scan date should be used as the date of recurrence or secondary malignancy.

In the absence of pathology to confirm the equivocal findings, these subjects will be censored at the date of last scan before anti-cancer therapy (if applicable). The last scan date includes the scan where the equivocal finding was noted.

For subjects identified as having the presence of disease at baseline by IRC review,

- Recurrence will be considered to have occurred on the date of randomization.

---

|           |   |                 |           |
|-----------|---|-----------------|-----------|

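### The one-year landmark analysis does not say whose recurrence excludes a patient; if only IRC recurrence does, patients taken off axitinib for an investigator-called recurrence stay in the short-treatment group and tilt the HR towards longer treatment

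*SAP*

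**What the plan says.** SAP 7.3.4 (Exploratory Analyses) plans a one-year landmark analysis within the axitinib arm. The grouping uses duration alone: "patients whose duration of treatment in less than or equal to one year will be compared to those whose duration of treatment is greater" than that. The reason for stopping plays no part. The inclusion rule is: "Only patients randomized to treatment with Axitinib who are alive, disease-free, and still in disease-free survival follow-up at one year will be included". Patients with recurrence, secondary malignancy or death before one year are left out, and so are those "otherwise censored for DFS due to start of new anticancer therapy, missed assessments, or lost to follow-up prior to one year". The output is medians with 95% CIs and an unstratified Cox HR with its CI. "A p-value will not be reported as this analysis is considered exploratory".

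The paragraph names no assessor. SAP 5.1 sets the default for the primary endpoint: "The primary DFS analysis will be based on assessment by the IRC". The subgroup section, SAP 7.3.2, does name the assessor: "DFS by IRC will be analyzed in the same way as the primary analysis".

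Protocol 6.5.1 opens its list with "Patients will be withdrawn from treatment in the case of", and the first item is recurrence or secondary malignancy, without requiring IRC confirmation. Waiting for the IRC before a treatment decision is encouraged, not required. Under Protocol 5.5.2 and 7.1, after an investigator-only call "the patient must continue to receive tumor assessments until the IRC determines recurrence or occurrence of a secondary malignancy".

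**The concern.** A landmark is used so that early failures cannot define the short-treatment group. It works only if everyone whose disease has already driven the stopping decision is removed at the landmark. With IRC-only exclusion, one kind of patient is missed: off drug before month 12 because the investigator called recurrence, still free of an IRC event, no new therapy started, scans continuing. That patient counts as at risk in the short-treatment group and is likely to become an IRC event at one of the next scans.

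The causal direction is then reversed, since recurrence caused the stopping, and the resulting error always favours longer treatment. Treatment may last from one to three years, and this is the only planned efficacy analysis by treatment duration. An HR below 1 produced this way could be mistaken for a benefit of extended axitinib.

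**Working it through.** **1. Design inputs reproduce.** The landmark paragraph states no figure, so the check reuses the DFS assumptions of Protocol 9.1 and SAP 3.3: two-year axitinib DFS of 79%, 61% and 51% in categories of 90%, 1% and 9%; exponential times; 23% dropout by 18 months; 700 patients 1:1, so 350 on axitinib.

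- Category HRs: ln 0.79/ln 0.70 = 0.66; ln 0.61/ln 0.35 = 0.47; ln 0.51/ln 0.33 = 0.61, as stated.
- Events (Freedman): (1.960 + 1.282)² × (1.654/0.346)² = 240.1. Multiplied by 1.017 for one O'Brien-Fleming look at 75%, this is 244.2, rounded up to the stated 245.

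**2. Timeline of an affected patient.** Scans fall at weeks 16, 32, 48 and 64. The landmark is 365.25/7 = week 52.18. If the investigator calls recurrence at week 48 and the IRC at week 64, the patient is off drug and free of an IRC event at the landmark, and has an event 64 − 52.18 = 11.8 weeks later.

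**3. How many such patients.** With a one-scan lead, they are the recurrences that the IRC dates at week 64, with onset between weeks 48 and 64 (0.920 and 1.227 years).

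- Yearly hazards, −ln(S)/2: 0.1179, 0.2471 and 0.3367.
- S(0.920) − S(1.227): 0.0319, 0.0582 and 0.0720.
- Weighted: 0.9 × 0.0319 + 0.01 × 0.0582 + 0.09 × 0.0720 = 0.0358, and 0.0358 × 350 = 12.5 patients.
- Not dropped out by one year: exp(−0.2614/1.5) = 0.840, leaving 10.5.
- Early-call share (assumed) 20%: 2.1 patients; 40%: 4.2. If half start new therapy (assumed), SAP 7.3.4 removes them, leaving about 1.05 and 2.1.

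**4. Effect on the HR.** The axitinib arm was simulated with the inputs above, 16-week scans and no effect of duration (200,000 patients per setting, scaled to 350). The HR is more than one year versus one year or less, one-scan lead:

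| Off drug by 1 year for other reasons (assumed) | 20% early, half start new therapy | 30% early, half | 20% early, none | 30% early, none |
|---|---|---|---|---|
| 10% | 0.83 | 0.81 | 0.75 | 0.70 |
| 25% | 0.94 | 0.92 | 0.92 | 0.84 |
| 40% | 0.98 | 0.92 | 0.94 | 0.89 |

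- With 40% called early and half starting new therapy, separate runs gave 0.84-0.91 at 20-40% off drug for other reasons, and down to 0.73 at 10%.
- If 80% start new therapy, the one-scan HRs at 10-30% early calls are 0.88-0.99.
- With a two-scan lead the range is 0.53-0.98. The lowest value needs 30% early calls, no new therapy and only 10% off drug for other reasons.
- With no early calls the HR is 1.00-1.02. After excluding investigator calls by one year it is 0.95-1.04 across all settings, so simulation error is a few hundredths.

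**5. Rough check of the middle case.** The simulated landmark set is about 259 patients, 65 of them in the short-treatment group when 25% stop for other reasons. Taking 55 events (middle of a simulated 45-65), the risk is 55/259 = 0.212, or 13.8 events among 65. Adding 1.05 patients who all have events gives 14.85/66.05 = 0.225, and 0.212/0.225 = 0.94, in line with the table.

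**6. Against sampling error.** SE(log HR) is about 1/√(55 × 0.25 × 0.75) = 0.31. A null HR of 0.94 is a shift of 0.06, or 0.2 SE. At 10% off drug the SE is 1/√(55 × 0.1 × 0.9) = 0.45, and a null HR of 0.73 is a shift of 0.31, or 0.7 SE.

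**The case against.** The case against has several parts, and much of it stands.

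- **Assessor.** A reader might infer that the plan uses IRC recurrence only. SAP 7.3.4 does not say so, and other sections name the IRC when they mean it. If investigator recurrence excludes, these patients are already out. This stands. What remains is that two programmers could build different sets from the same sentence, and SAP 5.1 makes the IRC reading the natural one.
- **New therapy and pathology.** The exclusion for new anticancer therapy removes some affected patients. Local pathology for a site-confirmed recurrence goes to the IRC oncologist; if accepted, the event is dated at specimen collection, often before the landmark. An equivocal scan later confirmed by pathology is dated back to the scan. These limits stand. The simulations do not model the pathology route, so they overstate the number affected to that extent. Imaging-only calls that the IRC confirms later are not covered.
- **Growth criteria.** A reader might infer that week-48 liver or node findings commonly straddle the landmark, because growth over four weeks is needed. The documents do not support this: Protocol 7.1 says findings that miss the site criteria should not alter therapy, and the imaging criteria for lung and central nervous system need no growth interval.
- **The cut.** Thirteen four-week cycles are 364 days, and SAP 7.4.3 counts 352 days or more as 12 months, so a reader might infer that the one-year cut is wrong. It is not. The 352-day rule serves descriptive exposure tables; used here, it would put a patient already off drug at the landmark into the longer-treatment group.
- **Consequence.** The analysis is exploratory, described as an association, has no p-value and feeds no decision rule. This stands, and it limits the weight of the point. Patients whose investigator call is never confirmed also add little bias.

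**Conclusion.** The point holds in a limited form. SAP 7.3.4 leaves the assessor open. On the IRC definition of DFS it retains a few patients whose recurrence caused the stopping, and the error runs one way, towards longer treatment.

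The null HR is about 0.73-0.97, with 1-2 patients per 350 affected and about 0.93 in a middle case. This assumes 20-40% of recurrences called one scan early, half of those patients starting new therapy, and 10-40% off drug for other reasons. None of these rates is in the documents, so the true bias may be negligible. It grows with a two-scan lead, with no new therapy or with a small short-treatment group. It is absent if investigator recurrence already excludes. In the middle case it is well inside the confidence interval.

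The documents do not support reading this as a flaw in the primary analysis, or as a bias of known or large size.

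**What to change.** In SAP 7.3.4:

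1. State the assessor, and exclude patients who, on or before the landmark, had a recurrence or secondary malignancy by either the IRC or the investigator, or who stopped study drug for that reason. All of this is known at the landmark, so the rule does not condition on later events.
2. Keep the one-year cut as written.
3. As a cheap addition, show the same analysis in the placebo arm. A similar HR there would point to selection rather than drug effect. It is an imperfect check, because reasons for stopping differ between arms.

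The cost is a change of wording and a repeated program on data already collected. The downside is a few fewer patients in the set. Confounding by who tolerates the drug remains, and the analysis stays exploratory.
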